6.0 Local Number of Subjects

Up to 200 subjects will be enrolled at the University at Buffalo (up to 400 nationally). The second site is located at Virginia Tech Carillon Institute, local PI, [name]. We expect about 25% of participants to meet our in-lab screening criteria, 20% of those participants subjects to drop out and about 80 subjects will complete the study. In addition, a small sample (approximately 4-6

subjects) will be assigned to be pilot participants to help with quality assurance and data validity procedures. Participants will be informed if they are a pilot participant at the time of consent.

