Measurements for blood HbA1c, blood pressure, cholesterol, height and weight measured to calculate BMI, measures of delay discounting, food demand, other executive functions (e.g. working memory), energy intake, physical activity, and medication adherence will be collected at baseline, 3 months, and 6 months. In response to the coronavirus mandatory closures, these assessment measures may also be recorded remotely. In the event that a participant must have assessment measures performed remotely, a staff member may conduct a conference call or video conference with the participant to instruct them on how to complete questionnaires and complete executive function tasks online via online survey (For example, on Qualtrics). The staff member may also instruct the participant on how to weigh themselves and observe the participant taking their weight at home via video conference. In order to collect A1c measures for remote

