14.0 Statistical Analysis Plan

Analytic plan is to use factorial ANCOVA to compare between group differences in different measures of DD, executive function, weight loss, changes in metabolic control, dietary composition, and physical activity for subjects randomly assigned BT-EFT/BT. Covariates will be used if significant differences between groups are observed in subject characteristics. We predict a main effect of EFT such that EFT will reduce the discounting, improve metabolic control, and increase weight loss compared to BT subjects.

The estimated sample size for this study is based on an ESD for reducing DD of 0.72 in obese/overweight subjects. In our pilot study of EFT vs control in a weight control program we observed even larger ESD of 1.64 for weight and 1.04 for energy intake. Based on ESD = 0.72 for DD, using power of 0.80 and alpha of 0.05, we can detect differences between groups in DD with 32 subjects per group, 64 total. Since we are anticipating 20% attrition for the field study, we will recruit 78 persons with prediabetes to start.

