16.0 Withdrawal of Subjects

Subjects who do not adhere to the protocol procedures and study instructions may be withdrawn from research analyses, as determined by the Principal Investigator and/or NIH Data Safety Committee. In addition to not adhering to study instructions, possible reasons for removal may include nonsystematic responding to questionnaires and HbA1c (blood sugar) levels that are not in the study prediabetes range. If a participant is withdrawn from the study without their consent, they will be debriefed about the nature of the study and be compensated for the amount of time spent in the study. We may also stop an ongoing session, or end participation in the study because we have collected all the information we need.

Participants will be debriefed about the nature of the study and the reason for their removal. No additional follow-up is needed.

Participants can withdraw from the research at any time. If participants withdraw, no further data will be collected, but any information that had been provided may be retained by the researcher and analyzed.

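### Section 14 gives the 3-month outcomes no role, so by default its ANCOVA would omit randomised participants who have no 6-month value

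*Combined protocol and SAP*

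**What the plan says.** - **Method.** Section 14.0 opens: "Analytic plan is to use factorial ANCOVA to compare between group differences in different measures of DD", and extends this to weight, metabolic control and other outcomes. Covariates enter only if the groups differ significantly. The section gives no analysis time point, analysis set, missing-data rule or sensitivity analysis.
- **Sample size.** "The estimated sample size for this study is based on an ESD for reducing DD of 0.72 in obese/overweight subjects". Then, "using power of 0.80 and alpha of 0.05", "we can detect differences between groups in DD with 32 subjects per group, 64 total".
- **Attrition.** The only provision in Section 14.0 is over-recruitment: "Since we are anticipating 20% attrition for the field study, we will recruit 78 persons with prediabetes to start".
- **Time points.** Section 2.0 states each of the three primary hypotheses for 6 months of treatment. Section 11.0 lists HbA1c, weight, delay discounting (DD) and other measures and ends: "medication adherence will be collected at baseline, 3 months, and 6 months". No analysis uses the 3-month values.
- **Randomisation.** Section 11.0 places it after about 6 weeks of treatment. The schedule table puts the 3-month assessment in weeks 11-12.
- **Withdrawal.** Section 16.0: "If participants withdraw, no further data will be collected". The same sentence goes on to allow data already given to be kept and analysed. Section 16.0 also lets participants be taken out of the analysis for non-adherence, at discretion.

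**The concern.** ANCOVA of a 6-month outcome needs a 6-month value. A randomised participant who attends at 3 months and then leaves contributes nothing unless the value is imputed or the model takes in earlier visits, and the plan provides for neither. With 20% attrition expected, two things are at stake.

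- **Bias.** In a weight-control programme, leaving may well depend on how the first months went. Completers in the two arms are then selected groups, and randomisation no longer protects the comparison.
- **Precision.** Information that the trial will already hold goes unused, in a design whose planned size leaves no reserve.

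**Working it through.** **1. The plan's own figure.** Inputs from Section 14.0: effect size 0.72, power 0.80, alpha 0.05. A two-sided two-sample t-test needs 31.27 per group, so 32 per group and 64 in total, as stated. A one-sided test would need only 24 to 25 per group, so the plan's alpha is two-sided. For 20% attrition, 64 / 0.8 = 80. The stated 78 is two short, which is immaterial. At 20% loss, 78 × 0.8 = 62.4 completers, or 31.2 per arm, with power 0.799. The sizing therefore rests on completers and has no slack.

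**2. Precision from the 3-month data.** Let m = 31.2 completers per arm, n₁ = participants per arm with a 3-month value, and r = the correlation between 3- and 6-month values (given baseline, if baseline is in the model). With monotone missing data, the likelihood estimate of a 6-month arm mean has variance, in SD² units,

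V = (1 − r²)/m + r²/n₁, against 1/m for completers only.

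The proportional reduction is r²(1 − m/n₁). The documents give neither r nor n₁, so I assume r = 0.3 to 0.9. For n₁ I take 39 (all drop-outs have 3-month data) or 35.1 (half do). The factor 1 − m/n₁ is then 0.200 or 0.111.

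| r | All: variance cut | Effective n per arm | Power | Half: variance cut | Power |
|---|---|---|---|---|---|
| 0.3 | 1.8% | 31.8 | 0.806 | 1.0% | 0.803 |
| 0.5 | 5.0% | 32.8 | 0.819 | 2.8% | 0.810 |
| 0.7 | 9.8% | 34.6 | 0.839 | 5.4% | 0.821 |
| 0.9 | 16.2% | 37.2 | 0.865 | 9.0% | 0.836 |

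Example for r = 0.7, all: 0.51/31.2 + 0.49/39 = 0.0289, and 1/0.0289 = 34.6. The formula ignores the estimation of the regression slope, so the gains are slightly optimistic. It also takes the 20% loss as falling after randomisation.

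**3. Bias.** All inputs here are assumptions: true effect 0.72 SD at 6 months and 0.36 SD at 3 months, about 20% drop-out, and log-odds of leaving that rise as the 3-month result worsens. If those who stay have a 3-month mean that is s SD better than their whole arm, their 6-month mean is r × s too favourable. The completers' difference is therefore 0.72 + r(s in BT-EFT − s in BT).

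With a slope of 1 per SD and r = 0.5, 0.7, 0.9, numerical integration gives:

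- **Same mechanism in both arms**, 20% overall: s differs by 0.040 between arms. 0.72 − 0.040r = 0.700, 0.692, 0.684.
- **Control arm only**, with random loss in BT-EFT: s = 0.173. 0.72 − 0.173r = 0.633, 0.599, 0.564. A simulation with 400,000 per arm gave 0.632, 0.599, 0.567, hence about 0.57 to 0.63.

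Over slopes of 0.5 to 1.5, the simulated ranges widen to about 0.67 to 0.72 (both arms) and 0.52 to 0.67 (control only). Conditioning on the 3-month value returned about 0.72 in every setting. If only BT-EFT lost its poor responders, the sign would reverse.

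**The case against.** A reader might infer that the sponsor has chosen a completers-only analysis at 6 months and will discard the 3-month data. The documents do not support that. Section 14.0 names no time point, and the 6 months come from the aims. No section restricts the analysis to completers. Section 16.0 allows data from people who withdraw to be analysed. Inflating recruitment for attrition is compatible with any later analysis, and the word factorial leaves open a second factor, possibly time.

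All of this stands as a limit on the claim, but it does not remove the problem. Permission to analyse earlier data is not a method that does so. A classical ANCOVA with time as a factor also drops incomplete cases.

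Four further points have weight:

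- **Delayed randomisation.** Those lost before about week 6 have no arm, and those who leave before weeks 11-12 have no 3-month assessment. The plan does not say whether its 20% includes them, so the recoverable share may be well below one in five.
- **Power for weight.** At the pilot effect size of 1.64 in Section 14.0, power with 31 per arm exceeds 0.999. The precision argument then matters little for weight, although it remains for DD, on which the trial is sized.
- **Size of the bias.** If the same mechanism acts in both arms, the bias is small.
- **Section 6.0.** It says "20% of those participants subjects to drop out and about 80 subjects will complete the study", against 64 in Section 14.0. With 80 completers, power would be about 0.89. The two sections must be reconciled.

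**Conclusion.** The concern holds as a default consequence of the plan. With ANCOVA as the only method, hypotheses at 6 months and no role for the 3-month data, randomised participants without a 6-month value would be left out. A better analysis of data already being collected is available.

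The precision gain is real but modest, at about 1% to 16% of variance. It depends on an unknown correlation and on how many drop-outs reach the 3-month visit after randomisation. The bias argument is the stronger one. The loss is small (about 0.68 to 0.70 against 0.72) if early results drive drop-out alike in both arms, and larger (about 0.57 to 0.63) if they do so in the control arm only. Which mechanism will operate is not known in advance.

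The sample size is not in error, and nothing here shows that the trial is undersized. The change should be made before analysis begins.

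**What to change.** In Section 14.0:

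1. Define the primary analysis set as all randomised participants, and reconcile the discretionary removal from analysis in Section 16.0 with it.
2. Make the primary analysis of weight, HbA1c and DD a likelihood-based repeated-measures model of the 3- and 6-month values. Include arm, visit, arm-by-visit, baseline value and site, and test the arm contrast at 6 months.
3. Add one missing-not-at-random sensitivity analysis in which unobserved outcomes are worse than the model predicts.
4. State whether the 20% attrition is counted from recruitment or from randomisation.

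The cost is SAP wording and a little more analysis work, with no new data. The model relies on data being missing at random given what was observed. That is an assumption, but a weaker one than an analysis of completers needs, and step 3 tests it. The model cannot recover people lost before randomisation.

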15.0 Provisions to Monitor the Data to Ensure the Safety of Subjects

Data will be reviewed weekly and secured in Division of Behavioral Medicine Research Lab. The Principal Investigator, [name], will be responsible for ensuring data integrity and safety monitoring for human subjects

who are involved in the research and may work with a Data Safety Officer consistent with our NIH DSMP.

Study questionnaires and measurements that are collected by study personnel will be reviewed and monitored.

This study poses no greater than minimal risk; therefore, there are no safety endpoints.

Participants will be encouraged to contact study personnel if they experience any problems or difficulties, and if any adverse events (AE) are reported, the study personnel contacted will record the AE. AE will be recorded as soon as they are reported, and the PI and study coordinator will be made aware. The study coordinator will summarize the AE in a memo; the participant will be called and the summary will be read to them to ensure that the information is accurate. The memo will then be submitted to the University at Buffalo IRB and the PI. If the PI, or the IRB decide that further action is warranted, the PI and study coordinator will then formulate and carry out a plan to respond to the AE. The study coordinator will write a memo summarizing such actions; this memo will then be forwarded to the IRB. Safety information will be collected and reported to both the UBIRB and the Safety Officer in the time frames outlined by the UBIRB.

Serious Events and Problems (SEP) will be monitored by the Principal Investigator and project coordinator as well as reported to both the IRB and the Safety Officer in the timeframes outlined by the IRB.

16.0 Withdrawal of Subjects

Subjects who do not adhere to the protocol procedures and study instructions may be withdrawn from research analyses, as determined by the Principal Investigator and/or NIH Data Safety Committee. In addition to not adhering to study instructions, possible reasons for removal may include nonsystematic responding to questionnaires and HbA1c (blood sugar) levels that are not in the study prediabetes range. If a participant is withdrawn from the study without their consent, they will be debriefed about the nature of the study and be compensated for the amount of time spent in the study. We may also stop an ongoing session, or end participation in the study because we have collected all the information we need.

Participants will be debriefed about the nature of the study and the reason for their removal. No additional follow-up is needed.

Participants can withdraw from the research at any time. If participants withdraw, no further data will be collected, but any information that had been provided may be retained by the researcher and analyzed.

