After the first several weeks of treatment (about 6 weeks), eligible participants will be randomized to one of two groups, BT-EFT or BT. Participants in both groups will first attend weekly group meetings followed by bi-weekly group meetings, and then monthly group meetings for up to 6 months. Group sessions may be audio or video recorded so that if a participant misses the meeting, they are able to receive the information and learn the materials on their own time. They will be provided general information on healthy diet, physical activity and medication adherence. During the in lab appointments participants will be taught a number of behavioral treatment techniques. The treatment includes: 1) The Traffic Light Diet, which utilizes RED, YELLOW, and GREEN labels for food to guide participants toward the goal of consuming low energy dense, low glycemic, high nutrient dense foods; 2) the Traffic Light Activity Program, which also utilizes RED, YELLOW and GREEN labels for different levels of caloric expenditure, and 3) a variety of behavioral techniques, including stimulus control, self-monitoring, goal setting, problem solving, resetting rewarding mechanisms by reducing need for immediate gratification, finding behavioral substitutes for highly reinforcing food, and EFT (for the intervention group).

During each treatment meeting, participants will be weighed and then have a group session that lasts up to 60 minutes either preceded or followed by a session with a case manager that may last up to 30 minutes. The group sessions review information about weight loss and maintenance and engage in group problem solving for participants who are struggling with behavior change. During the individual meeting with their case manager, participants are taught behavior change techniques and review and address diet and activity self-monitoring and any barriers to adherence with the weight-loss behaviors.

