After participants are randomized, participants in the EFT group will be asked to generate episodic cues similar to the tasks used in our previous studies on EFT's effect (Daniel et al., 2013). Each group will list and describe events for different time periods. The episodic component of the thinking task will occur while the participants are asked to describe what they are imagining about each event (e.g., vacations, weddings, parties, and so forth). EFT participants will list positive future events they are looking forward to and list events that could happen at different general future time points (e.g., 1 month, 2-6 months, 7-12 months). In contrast, the BT group will not generate any cues. All EFT participants may rate the salience, valence, arousal, feasibility and vividness of each event and events with the highest ratings for vividness will be used in the generation of episodic cues. An "imagery" score may be calculated by averaging the frequency/vividness scores for each event. Reductions in rate of discounting occur at higher levels of episodic imagery (Peters & Buchel, 2010). Additionally, participants may record their highest rated events into audio cues.

Experimenters will train participants in the EFT group on how to retrieve cues from their cell phone or alternative internet accessible device (e.g. laptop, tablet, desktop computer), to pay attention to and think about the cues, and how to adhere to the study's expectations for utilizing the cues. If participants do not have an internet accessible device one may be provided to them (e.g. smartphone) for the duration of the study at no cost to them. Participants may be prompted several times a day to use their cues and instructed to use their cues any time that need to, especially around eating episodes, using the thought training website – Mobile Audio Management and Response Tracker (MAMRT) (Sze, Daniel, Kilanowski, Collins, Epstein, 2015).

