Ecological momentary intervention (EMI) uses mobile technology to deliver interventions to individuals during their everyday lives (i.e. in real time) and in their natural settings (i.e. real world). EMIs enhance the ability to influence behavior in real-world contexts as participants often experience tempting food situations in their natural environments. In this study, the EMI will involve daily prompts to use EFT cues and answer questions about their cues using the thought training (MAMRT) (Sze, Daniel, Kilanowski, Collins, Epstein, 2015). MAMRT will deliver cues/prompts daily to participants. Participants will also be able to access MAMRT and their EFT cues as many times a day as they desire.

During individual sessions case managers may review progress, habit changes, medication adherence, and use of EFT. In the control group participants will not use cues but will still be prompted to log into the MAMRT website and answer questions about their eating behaviors. Participants in the control group will otherwise engage in the same tasks. During weeks when participants do not visit the lab and do not meet with their case manager, they may be contacted by phone, email, or text by their case manager to check in and review progress, similar to an in-person case management meeting.

In response to the coronavirus pandemic, we are enacting preventative measures to ensure both participants and employees limit exposure. For group sessions and case management sessions, this may entail conducting group sessions by sending

participants a recorded video or using a password-protected video conference (Such as via Webex or Zoom Meeting) on a secured network. In this event, a link with a password to access the secured meeting room would be sent to participants and necessary staff. Case management sessions intended to occur in-person may also be carried out via secured video conference or by phone. As is the case for in-person group sessions, video-conference group sessions may be audio or video recorded so that if a participant misses the meeting, they are able to receive the information and learn the materials on their own time.

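### Section 16.0 permits discretionary removal of non-adherent participants from the analyses after randomisation, and Section 14.0 defines no all-randomised set to override it

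*Combined protocol and SAP*

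**What the plan says.** Section 16.0 (Withdrawal of Subjects) contains the permission: "Subjects who do not adhere to the protocol procedures and study instructions may be withdrawn from research analyses". The same sentence leaves the choice to named parties, without criteria: "as determined by the Principal Investigator and/or NIH Data Safety Committee". The section adds that "possible reasons for removal may include nonsystematic responding to questionnaires and HbA1c (blood sugar) levels that are not in the study prediabetes range", and says that removed participants need no further follow-up. For people who withdraw of their own accord, it says that "any information that had been provided may be retained by the researcher and analyzed".

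Section 11.0 (Procedures Involved) places randomisation some way into treatment: "After the first several weeks of treatment (about 6 weeks), eligible participants will be randomized to one of two groups". After that point BT-EFT participants are trained in "how to adhere to the study's expectations for utilizing the cues". For the other arm: "In the control group participants will not use cues but will still be prompted to log into the MAMRT website". The next sentence says that control participants otherwise do the same tasks. Section 11.0 also schedules outcome assessments at baseline, 3 months and 6 months.

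Section 14.0 (Statistical Analysis Plan) plans a factorial ANCOVA "for subjects randomly assigned BT-EFT/BT". It names no intention-to-treat or other analysis set, and no method for missing outcomes.

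**The concern.** A randomised comparison is protected against selection only if the people analysed are the people randomised. Section 16.0 lets someone drop randomised participants for how they behaved after assignment, and it gives no criterion that could be checked later. The cut could fall at any level of adherence and at any time up to month 6. Nothing requires the person deciding to be unaware of arm or outcome.

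Adherence is plausibly related to weight loss, glycaemic control and delay discounting (DD), which together form the primary endpoint in Section 3.0. BT-EFT has one more instruction to fail than BT, namely cue use. If poor adherers were removed more often from one arm, that arm would look better than it is. The published result could not show whether a difference came from treatment or from selection.

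**Working it through.** **The plan's own figure.** Section 14.0 gives a standardised effect of 0.72 for DD, power 0.80, alpha 0.05, 32 per group and 78 recruited for 20% attrition. A two-sided two-sample t test needs 31.27, so 32 per group, and has power 0.809 at that size. The stated 32 reproduces. A one-sided test needs about 25 and does not. Applying the attrition to the recruitment target gives 78 × 0.80 = 62.4, or about 31 per arm (power 0.796). The proposed fix changes none of these inputs.

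**Reading the passages together.**
1. The key sentence in Section 16.0 concerns analyses, not only attendance.
2. It concerns people who do not adhere. The team's judgement of likely adherence is a separate step, made at screening before baseline (Section 9.0).
3. Randomisation comes at about week 6, so unless limited the permission covers the rest of the 6 months.
4. Section 14.0 settles which arm a participant is counted in. It does not say that every randomised participant is counted.

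**How large could the effect be?** The documents contain no adherence data, so this is an illustration and every input below is assumed except the 31 per arm:
- no true difference, outcome SD 1, scored so that higher is better;
- correlation r between adherence and outcome of 0.3 or 0.5, the same in both arms;
- the least adherent fraction f of an arm always removed;
- an unadjusted two-sample t test in place of the ANCOVA.

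Mean outcome of those kept in an arm = r × φ(z_f)/(1 − f).
- f = 10%: 0.1755/0.9 = 0.195, giving 0.058 (r = 0.3) or 0.097 (r = 0.5).
- f = 20%: 0.2800/0.8 = 0.350, giving 0.105 or 0.175.

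The shift is the BT-EFT value minus the BT value. Numbers kept are 31 (0%), 28 (10%) and 25 (20%). Type I error comes from the non-central t with non-centrality = shift/√(1/n₁ + 1/n₂). For 10% of BT and 20% of BT-EFT at r = 0.5: 0.077/√(1/25 + 1/28) = 0.077/0.275 = 0.28 on 51 degrees of freedom, two-sided 0.0588.

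| Removed (BT / BT-EFT) | r | Shift (SD) | Two-sided type I error | Favouring BT-EFT (nominal 0.025) |
|---|---|---|---|---|
| 10% / 20% | 0.3 | 0.046 | 0.0532 | 0.036 |
| 10% / 20% | 0.5 | 0.077 | 0.0588 | 0.046 |
| 0% / 10% (bound) | 0.3 | 0.058 | 0.0556 | 0.041 |
| 0% / 10% (bound) | 0.5 | 0.097 | 0.0656 | 0.056 |
| 0% / 20% (bound) | 0.3 | 0.105 | 0.0670 | 0.058 |
| 0% / 20% (bound) | 0.5 | 0.175 | 0.0980 | 0.093 |

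Reversing the fractions (20% of BT, 10% of BT-EFT) gives the same size of shift against BT-EFT. Equal removal gives no mean shift when r is the same in both arms.

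**Sensitivity.** The documents do not say whether removals come on top of attrition. Starting from 39 per arm, two-sided error is 0.054 to 0.061 for 10%/20% and 0.057 to 0.111 for the bounding case. With r of 0.1 to 0.2 and 31 per arm, the 10%/20% case gives only 0.0503 to 0.0514. Simulation of the 10%/20% case at r = 0.3 to 0.5 gives 0.056 to 0.066, but equal 10% removal alone gives 0.051 to 0.056, so part of that excess is not due to the imbalance.

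**The case against.** The best defence has four parts.

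- **Assignment wording.** The ANCOVA is for participants as randomly assigned, which fits an all-randomised analysis. It does fix the grouping, but it says nothing that cancels the express permission in Section 16.0.
- **Common tasks.** Section 11.0 says control participants otherwise do the same tasks, and the first weeks of treatment precede randomisation. This stands. Cue use is the only added demand the documents show for BT-EFT, no minimum is set for it, and BT participants can also fail to adhere. A large imbalance in exclusions is possible but has no support in the text.
- **Size.** Outside the bounding case the shifts are under 0.08 SD against a design effect of 0.72, and all rest on assumed inputs. This also stands, so the figures should not carry the point. How the planned ANCOVA would change them is unknown.
- **Oversight.** A safety committee may be involved. But the wording is and/or, so the investigator may decide alone.

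A reader might infer that exclusions will be made with knowledge of arm. The documents are silent on blinding, which is not the same thing. A reader might also infer that removal for an out-of-range HbA1c selects on a primary outcome. Section 16.0 does not say which reading counts or whether removal there means exclusion from analysis. Section 11.0 uses HbA1c as an eligibility check before randomisation, and Section 17.0 mentions only referral. That is a matter for clarification, not a demonstrated bias.

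**Conclusion.** The concern holds in a limited form. A stated rule allows randomised participants to be left out of the analyses for non-adherence, at discretion and without criteria, and no defined analysis set overrides it. The resulting bias could run in either direction. It would be tempting to conclude that the trial will be analysed per protocol, or that its result will favour BT-EFT. The documents support neither: the wording is permissive, and no exclusion is reported or planned.

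Under the assumptions shown, a moderate imbalance moves the difference by about 0.05 to 0.08 SD (type I error 0.053 to 0.059), and the one-sided bound by 0.06 to 0.18 SD (0.056 to 0.098). The case for change rests on the undefined analysis population rather than on these numbers, and the remedy is inexpensive.

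**What to change.** **Section 14.0.** State: *The primary analysis includes all randomised participants in the arm assigned, whatever their adherence.* Keep the planned ANCOVA, use all available 3- and 6-month outcomes, and name a likelihood-based or multiple-imputation method for missing outcomes.

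**Section 16.0.** Replace the permission to exclude from analyses with a statement that non-adherence after randomisation does not remove a participant's data from the primary analysis. Keep stopping participation and exclusion from analysis as separate matters. Merely deleting the reference to analyses would not do: the sentence would become a rule for ending participation and, with no follow-up required, would exchange selective exclusion for selective missing data.

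**Secondary analyses.** Make adherence-based exclusions labelled sensitivity analyses. For nonsystematic responding, fix the criteria in advance and apply them blind to arm.

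**For the sponsor to reconcile.** The statement in Section 16.0 that removed participants need no further follow-up should be squared with the 3- and 6-month assessments in Section 11.0, for those who are removed but still consent to assessment. The sponsor should also clarify whether removal for out-of-range HbA1c refers only to eligibility readings before randomisation.

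**Cost.** Sample size and visit schedule are unchanged. The estimate will be somewhat diluted by non-adherers, and obtaining outcomes from people who stop treatment takes modest effort.
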